6.5 Rituximab

There will be no planned dose reduction for rituximab. Rituximab infusion should be interrupted for severe reactions, e.g., rapid tumor lysis. Treatment of infusion-related symptoms with diphenhydramine and acetaminophen is recommended. Additional treatment with bronchodilators or IV saline may be indicated. Epinephrine, antihistamines, and corticosteroids should be available for immediate use in the event of a hypersensitivity reaction to rituximab (e.g., anaphylaxis). In most cases, the infusion can be resumed at a 50% reduction in rate (e.g., from 100mg/hr to 50mg/hr) when symptoms and laboratory abnormalities have completely resolved.

Infusions should be discontinued in the event of serious or life-threatening cardiac arrhythmias. Subjects who develop clinically significant arrhythmias should undergo cardiac monitoring during and after subsequent infusions.

In patients with an absolute lymphocyte count $> 25,000/\text{microliter}$, contact the principal investigator prior to first rituximab infusion. Patients should be monitored closely for tumor lysis syndrome and should receive appropriate supportive care (e.g., allopurinol, intravenous hydration, additional laboratory test monitoring, etc.).

6.6 Obinutuzumab

There will be no dose modifications of obinutuzumab. Treatment with obinutuzumab should be delayed for Grade 4 hematologic toxicity or clinically significant Grade ≥ 3 non-hematologic toxicity experienced at the time of scheduled dosing.

For hematologic toxicities, patients who experience Grade 4 toxicities should have their doses of obinutuzumab delayed for monitoring of resolution or improvement of toxicity. Dosing may resume upon the resolution of hematologic toxicity to Grade ≤ 3 or baseline status.

For non-hematologic toxicities, dosing may resume only upon resolution to Grade ≤ 2 or baseline. In addition, resumption of dosing without complete resolution of toxicity may be considered only upon careful weighing of the benefits and risks to the patient and agreement between the investigator and the Sponsor-investigator.

For management of symptomatic AEs (including IRRs), see below.

- **Grade 4 (life threatening):** Stop infusion and permanently discontinue therapy.
- **Grade 3 (severe):** Temporarily interrupt infusion and treat symptoms. Upon resolution of symptoms, restart infusion at no more than half the previous rate (the rate being used at the time that the IRR occurred). If patient does not experience any further IRR symptoms, infusion rate escalation may resume at the increments and intervals as appropriate for the treatment dose. If the patient experiences a second occurrence of a Grade 3 IRR, stop infusion and permanently discontinue therapy.
- **Grade 1&2 (mild and moderate):** Reduce infusion rate and treat symptoms. Upon resolution of symptoms, continue infusion. If patient does not experience any IRR symptoms, infusion rate escalation may resume at the increments and intervals as appropriate for the treatment dose.

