5.1.1 Induction

Cohort A: ALR cohort

- Cycles 1-12, 1 cycle = 28 days
- Acalabrutinib 100 mg BID continuous
- Lenalidomide on days 1-21 (15 mg for cycle 1, then escalate as tolerated to 20 mg)
- Rituximab 375 mg/m² on days 1, 8, 15, 21 of cycle 1 then day 1 of cycle 4, 6, 8, 10, 12

Cohort B: ALO feasibility cohort

- Cycles 1-12, 1 cycle = 28 days
- Acalabrutinib 100 mg BID continuous
- Lenalidomide on days 1-21 (15 mg for cycle 1, then escalate as tolerated to 20 mg)
- Obinutuzumab on days 1, 8, 15 of cycle 1, day 1 of cycles 2-6, then every 2 cycles

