6.4.1 Neutropenia

For grade 3 or 4 neutrophil count decreased on day 1 of a cycle, delay lenalidomide and acalabrutinib until ANC improves to \leq grade 2, then resume lenalidomide and acalabrutinib with one dose level reduction (Table 7) for all subsequent cycles.

For grade 3 or 4 neutrophil count decreased during a cycle, interrupt lenalidomide and acalabrutinib for the remainder of the cycle. Resume lenalidomide and acalabrutinib (if ANC \leq grade 2) at the next cycle with one dose level reduction (Table 7) for all subsequent cycles.

For febrile neutropenia at any time during a cycle, interrupt or delay lenalidomide and acalabrutinib until toxicity improves to \leq grade 2, then resume lenalidomide and acalabrutinib with one dose level reduction (Table 7) for all subsequent cycles.

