6.7 Instruction for Initiation of a New Cycle

A new course of treatment with all study medications may begin on the scheduled Day 1 of a new cycle if:

- The ANC is $\geq 1000/\text{mm}^3$;
- The platelet count is $\geq 50,000/\text{mm}^3$;
- Any drug-related rash or neuropathy that may have occurred has resolved to \leq grade 1 severity;
- Any other drug-related adverse events that may have occurred have resolved to \leq grade 2 severity;
- Completion of 7-day rest period following the last dose of lenalidomide from previous cycle.

If these conditions are not met on Day 1 of a new cycle, the subject will be evaluated weekly and a new cycle of treatment will not be initiated until the toxicity has resolved as described above.

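### With a grade 3 neutrophil or platelet count on Day 1, section 6.6 permits an obinutuzumab dose that section 6.7 forbids, and no text says which section governs

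*Combined protocol and SAP*

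**What the plan says.** Four parts of section 6 bear on whether obinutuzumab is given on Day 1 of a cycle.

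- **6.6 Obinutuzumab.** "Treatment with obinutuzumab should be delayed for Grade 4 hematologic toxicity or clinically significant Grade" 3 or higher non-hematologic toxicity, judged when the dose is due. For blood counts: "Dosing may resume upon the resolution of hematologic toxicity to Grade ≤ 3 or baseline status".
- **6.7 (new-cycle rule).** "A new course of treatment with all study medications may begin on the scheduled Day 1 of a new cycle if" ANC is at least 1000/mm³, platelets are at least 50,000/mm³, and three further conditions are met. If they are not, the subject is evaluated weekly and "a new cycle of treatment will not be initiated until the toxicity has resolved as described above".
- **6.4.1 Neutropenia.** "For grade 3 or 4 neutrophil count decreased on day 1 of a cycle, delay lenalidomide and acalabrutinib" until the count recovers to grade 2 or better. Section 6.4.2 does the same for platelets. Neither names the antibody.
- **6.3.2 (lenalidomide).** When a new cycle is delayed, all study medications restart together on the new Day 1.

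The schedule in 5.1.1 is: "Obinutuzumab on days 1, 8, 15 of cycle 1, day 1 of cycles 2-6, then every 2 cycles". Table 4 in 5.3.4 starts the two-monthly dosing at cycle 8. In maintenance (5.1.2) the antibody is due on Day 1 of even-numbered cycles.

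**The concern.** Section 6.6 sets its hematologic limit between grades 3 and 4. Section 6.7 sets its limit between grades 2 and 3, and it covers all study medications. A grade 3 count therefore falls on different sides of the two limits. After cycle 1 every scheduled obinutuzumab dose is on a Day 1, so both sections apply to the same dose.

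A site that follows the drug-specific section may infuse a patient whom a site following the new-cycle section would hold. In a multicenter cohort of 10 patients, that makes obinutuzumab exposure, and the cytopenias recorded under it, partly a product of which section a site read. It also leaves no clear standard for deciding whether a dose given, or a dose held, was a protocol deviation.

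**Working it through.** The plan offers no figure to reproduce. The check compares thresholds and counts doses.

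**Grade cut-offs, from the protocol itself.** Section 6.1 puts grade 3 or worse neutropenia at ANC below 1,000/mm³ and grade 4 at below 500. It puts grade 4 thrombocytopenia at platelets below 25,000/mm³. Table 6 in 6.3.2 puts grade 3 or worse thrombocytopenia at below 50,000. The limits in 6.7 therefore correspond to grade 2 or better for both counts.

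**The sections side by side, Day 1 of a cycle after cycle 1 with obinutuzumab due:**

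| Day 1 count | Section 6.6 | Section 6.7 |
|---|---|---|
| ANC ≥1000 and platelets ≥50,000 | No delay for counts | Counts do not block the cycle |
| ANC 500-999 or platelets 25,000-49,999, neither grade 4 | No delay; resumption permitted | Cycle not started |
| ANC <500 or platelets <25,000 | Delay | Cycle not started |

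The sections part only in the middle row. Another drug-related grade 3 hematologic event, such as anemia, falls in the same gap, because 6.7 requires other drug-related events to be at grade 2 or lower.

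**The baseline exception.** Section 6.6 allows resumption at baseline status and 6.7 has no such exception. This does not widen the range for the two counts, since eligibility (3.2) requires ANC of at least 1000 and platelets of at least 75,000.

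**Doses exposed.** The cycle 1 Day 1-2 split is counted as one dose.

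- Cycle 1: Days 1(-2), 8 and 15 = 3 doses. None starts a new cycle after an earlier one, so the conflict does not reach them.
- Cycles 2 to 6, Day 1: 5 doses.
- Cycles 8, 10 and 12, Day 1: 3 doses.
- Total induction doses: 3 + 5 + 3 = 11. Exposed: 5 + 3 = 8.
- Maintenance: all doses fall on Day 1 (cycles 14, 16, 18 and so on), so all are exposed.

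**Search for a tie-breaker.** The introduction to section 6 lists the rules without ranking them. Sections 6.4.1 and 6.4.2 are silent on the antibody. Section 6.3.2 points towards a joint restart, but it cites section 6.5 for the new-cycle conditions, and 6.5 is now the rituximab section. Section 5.3.4 says a missed obinutuzumab dose is to be given as soon as possible, without saying whether a dose withheld under 6.7 counts as missed. After 24 cycles the oral drugs may be stopped while the antibody continues (5.1); no text says which section governs then.

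**The case against.** The strongest reply is that the two sections can both be obeyed. Section 6.6 says when to delay and when dosing may resume; it never orders a dose at grade 3. Section 6.7 is a gate on the cycle, and if the cycle has not begun, its Day 1 dose is not yet due. Holding satisfies both. Section 6.3.2 is consistent with this, and 6.4.1 and 6.4.2 use the same grade 2 limit as 6.7. They name only the oral drugs, and Table 7, to which they refer, covers only those drugs; they do not say that the antibody goes ahead. On this view 6.6 keeps a purpose for the infusions within cycle 1.

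Much of this stands. A reader might infer that the protocol orders a dose in one place and forbids it in another. It does not: one section permits and the other prohibits. But the reconciling reading is nowhere written. The trigger in 6.6 applies at the time of scheduled dosing, with no restriction to doses within a cycle. If 6.7 always prevails, the Grade 3 resumption limit in 6.6 has no effect on an ANC or platelet hold at any dose after cycle 1. A site that follows 6.6 as written has a reasonable basis for treating.

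Two further inferences are tempting and unsupported.

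- **Number of patients.** The background cites grade 3/4 neutropenia of 16% with lenalidomide-obinutuzumab in follicular lymphoma (2.5) and 50% with lenalidomide-rituximab in MCL (2.2.1). Applied to 10 patients, these give 1.6 to 5. They are rates from other regimens, not Day 1 rates, and they include grade 4, where both sections hold. They do not estimate how many ALO patients would meet the conflict.
- **The feasibility verdict.** The first ALO condition covers only the 28 days of cycle 1, before the conflict can arise. The second counts patients who stop treatment for adverse events in the first year. A held infusion is not a stop. Removal for a cycle delay of more than 4 weeks (6.3.1) turns on a delay that 6.4 and 6.7 impose on the oral drugs under either reading. No route from the ambiguity to that count is shown.

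**Conclusion.** The inconsistency is real. On Day 1 of any cycle after the first in which obinutuzumab is due, an ANC of 500-999 or platelets of 25,000-49,999 leaves section 6.6 permitting a dose that section 6.7 forbids. It can arise at 8 of 11 induction doses and at every maintenance dose. The conclusion rests on the protocol's own grade cut-offs and schedule, and on the absence of any statement of precedence.

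The number of patients affected is unknown, and no effect on the feasibility conditions has been shown. The primary endpoint concerns ALR and is untouched. The point still deserves correction before ALO dosing data are interpreted, because sites following the text can handle the same cytopenic patient differently. Which rule is right is a clinical matter on which this review takes no position.

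**What to change.** Reconcile 6.6 and 6.7 so that one stated Day 1 count rule governs obinutuzumab, and say which section prevails. State explicitly whether the antibody is given or held when the oral drugs are delayed, and which rule applies once the oral drugs have been stopped and the antibody continues alone. Add a cross-reference in 6.4.1, 6.4.2 and 6.3.2, and correct the pointer in 6.3.2 from section 6.5 to the new-cycle section. The clinical team decides the rule. The cost is amendment wording, with no added visits, tests or patients.

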6.7 Instruction for Initiation of a New Cycle

A new course of treatment with all study medications may begin on the scheduled Day 1 of a new cycle if:

- The ANC is $\geq 1000/\text{mm}^3$;
- The platelet count is $\geq 50,000/\text{mm}^3$;
- Any drug-related rash or neuropathy that may have occurred has resolved to \leq grade 1 severity;
- Any other drug-related adverse events that may have occurred have resolved to \leq grade 2 severity;
- Completion of 7-day rest period following the last dose of lenalidomide from previous cycle.

If these conditions are not met on Day 1 of a new cycle, the subject will be evaluated weekly and a new cycle of treatment will not be initiated until the toxicity has resolved as described above.

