6.2 Acalabrutinib

Dose modifications for the following treatment-emergent toxicities are provided in Table 4:

- Grade 4 neutropenia (< 500/µL) for > 7 days
- Grade 3 thrombocytopenia in presence of significant bleeding
- Grade 4 thrombocytopenia
- Grade 3 or 4 nausea, vomiting, or diarrhea, if persistent despite optimal antiemetic and/or anti-diarrheal therapy

- Any other Grade 4 toxicity or unmanageable Grade 3 toxicity

Table 4. Drug Modification Actions for Acalabrutinib

Occurrence	Action
1 st – 2 nd	Hold acalabrutinib until recovery to Grade \leq 1 or baseline; may restart at original dose level
3 rd	Hold acalabrutinib until recovery to Grade \leq 1 or baseline; restart at one dose level lower (100 mg QD)
4 th	Discontinue acalabrutinib

If acalabrutinib is reduced for apparent treatment-related toxicity, the dose need not be re-escalated, even if there is minimal or no toxicity with the reduced dose. However, if the subject tolerates a reduced dose of acalabrutinib for \geq 4 weeks then the dose may be increased to the next higher dose level, at the discretion of the investigator. Such re-escalation may be particularly warranted if further evaluation reveals that the AE that led to the dose reduction was not treatment-related. The maximum dose of acalabrutinib is 100 mg BID.

Treatment with acalabrutinib should be withheld for any unmanageable, potentially study drug-related toxicity that is Grade \geq 3 in severity. Acalabrutinib should be discontinued in the event of an acalabrutinib toxicity lasting more than 28 day. Any other clinically important events where dose delays may be considered appropriate must be discussed with the Principal Investigator.

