Non-blistering rash Grade 3	
 If Grade 3, hold (interrupt) lenalidomide dose. Follow weekly. If the toxicity resolves to \leq grade 1 prior to Day 21 of the current cycle, restart lenalidomide at next lower dose level and continue through the scheduled Day 21 of the current cycle. Otherwise, omit for remainder of cycle and reduce the dose of lenalidomide by 1 dose level at the start of the next cycle. Omitted doses are not made up.
Desquamating (blistering) rash- any Grade	
 Discontinue lenalidomide. Remove patient from study.

Table 6. Lenalidomide Dose Modifications	
NCI CTC Toxicity Grade	Dose Modification Instructions
Neuropathy Grade 3	
 • If Grade 3, hold (interrupt) lenalidomide dose. Follow at least weekly. • If the toxicity resolves to \leq grade 1 prior to Day 21 of the current cycle, restart lenalidomide at next lower dose level and continue through the scheduled Day 21 of the current cycle. Otherwise, omit for remainder of cycle and reduce the dose of lenalidomide by 1 dose level at the start of the next cycle. Omitted doses are not made up.
	
 • If Grade 4, discontinue lenalidomide. Remove patient from study.
Venous thrombosis/embolism \geq Grade 3	
 • Hold (interrupt) lenalidomide and start therapeutic anticoagulation, if appropriate. • Restart lenalidomide at investigator's discretion (maintain dose level). • See Anticoagulation Consideration (Section 8.1.1)
Tumor lysis syndrome \geq Grade 3	
 • Interrupt therapy. • May resume study drug when the TLS resolves to \leq Grade 1 (decrease one dose level)
Tumor Flare \leq Grade 2	
 • at the investigators discretion, may initiate therapy with corticosteroid, NSAIDs and/or Narcotics • Continue Study drug
Tumor Flare Grade 3 or 4	
 • Hold (interrupt) dose and start corticosteroids, NSAIDs and/or Narcotics. • When toxicity resolves to \leq grade 1 restart at next lower dose level

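### Sections 6.7 and 6.3.2 restart all study drugs at grade 2 or less, but Section 6.2 (acalabrutinib) and Table 6 (tumor lysis, tumor flare) require grade 1 or less, and no rule of precedence is given

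*Combined protocol and SAP*

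**What the plan says.** Section 6.7 sets the conditions for starting a cycle and applies them to every drug at once: "A new course of treatment with all study medications may begin on the scheduled Day 1 of a new cycle if" the listed conditions hold. Rash and neuropathy must have come down to grade 1 or less. For everything else the entry reads "Any other drug-related adverse events that may have occurred have resolved to" grade 2 or less.

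Section 6.3.2 covers interruptions that delay a cycle. Once toxicity has resolved enough for a new cycle, the restart day becomes Day 1 and all study medications restart on it. The section it cites for the criteria is 6.5, which deals with rituximab. The criteria are in 6.7.

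Section 6.2 has its own table for acalabrutinib. (It is numbered Table 4, as is the obinutuzumab schedule in 5.3.4.) At the first three occurrences the action is "Hold acalabrutinib until recovery to Grade" 1 or less, or baseline. The non-hematologic triggers are grade 3 or 4 nausea, vomiting or diarrhea that persists under optimal treatment, any other grade 4 toxicity, and grade 3 toxicity that cannot be managed.

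Table 6, for lenalidomide, says of tumor lysis syndrome of grade 3 or higher: "May resume study drug when the TLS resolves to" grade 1 or less. It sets the same grade for tumor flare of grade 3 or 4. For other non-hematologic toxicity of grade 3 or higher it allows restart at grade 2 or less.

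**The concern.** A patient recovering from one of these severe events can meet the general rule for restarting every drug and still fail the drug-specific rule for one of them. Section 13 describes a multi-institution study, so different sites could treat the same patient differently and each could cite the protocol.

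This is first a safety matter, because the instruction on when to re-expose a patient is contradictory. It also bears on interpretation. Safety and tolerability of ALR is a secondary objective (Section 1.2), and exposure, holds and dose interruptions would partly reflect which section a site followed. The primary analysis of MRD-negative CR in Section 11.3.1 does not use these thresholds.

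**Working it through.** The plan states no figure to reproduce, so the check sets the rules side by side.

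| Source | Drug | Event | Grade needed to restart |
|---|---|---|---|
| 6.7 | all study drugs | drug-related rash or neuropathy | 1 or less |
| 6.7 | all study drugs | other drug-related events | 2 or less |
| 6.3.2 text | all study drugs | any event delaying a cycle | as for a new cycle |
| 6.2, Table 4 | acalabrutinib | listed severe toxicities | 1 or less, or baseline |
| Table 6 | lenalidomide | tumor lysis of grade 3 or higher; flare of grade 3 or 4 | 1 or less |
| Table 6 | lenalidomide | other non-hematologic, grade 3 or higher | 2 or less |
| 6.6 | obinutuzumab | non-hematologic | 2 or less, or baseline |

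**Where the rules agree.** For rash, Section 6.4.3 and Table 6 both use grade 1, as 6.7 does. For neuropathy, Table 6 and 6.7 agree. For other non-hematologic toxicity, lenalidomide (Table 6) and obinutuzumab (6.6) match the grade 2 limit in 6.7.

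**Where they conflict.** There are two places, and in each the difference is 2 − 1 = 1 grade:

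- acalabrutinib after a trigger listed in 6.2, when baseline is below grade 2;
- resumption under Table 6 after severe tumor lysis or tumor flare.

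**Case 1: delayed cycle, diarrhea.** A patient has grade 3 diarrhea that persists under optimal treatment, so 6.2 is triggered. It is still grade 3 on the scheduled Day 1, so 6.7 delays the cycle. It then falls to grade 2, and baseline was below grade 2.

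- 6.7: the condition is met and all drugs may begin.
- 6.3.2: this becomes Day 1 and all drugs restart.
- Table 6, other non-hematologic row: lenalidomide may restart.
- 6.2: acalabrutinib stays on hold.

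For acalabrutinib, 6.3.2 and 6.2 give opposite instructions on the same day.

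**Case 2: delayed cycle, flare.** A grade 3 tumor flare delays a cycle and falls to grade 2. Under 6.7 and the text of 6.3.2 all drugs restart. Table 6, in that same subsection, waits for grade 1 or less.

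**Search for a tie-breaker.** Nothing in Section 6 ranks these rules. The one link between them, the reference in 6.3.2, leads to the wrong section. The same gap appears with cytopenias, which lie outside this point: for grade 4 thrombocytopenia, 6.2 holds acalabrutinib to grade 1 or less or baseline, while 6.4.2 resumes it at grade 2 or less.

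**The case against.** The best defense is that the rules are layered. The opening of Section 6 distinguishes instructions for initiating a cycle from dose modifications during one. Section 6.7 is permissive: it says a course may begin, not that a held drug must be resumed. Table 4 and Table 6 are drug-specific. On that view 6.7 is a general gate and a stricter hold on one drug operates inside it.

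This is a plausible intent. Where 6.7 is met on the scheduled Day 1, the texts can be read that way. Two things count against it as a full answer. First, no section states it, and 6.7 speaks of all study medications without exempting a drug on hold. Second, it fails for a delayed cycle, because 6.3.2 says that all drugs will restart, not that they may. The hold in 6.2 is also defined by recovery and not by cycle day, so it carries across Day 1.

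Other parts of the defense stand in full. The nausea, vomiting and diarrhea trigger in 6.2 requires persistence despite optimal treatment, so grade 3 diarrhea that treatment controls does not engage that trigger. The baseline alternative removes the conflict for a patient whose baseline was already grade 2. Different grades for different toxicities within Table 6 are not a contradiction in themselves.

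**Conclusion.** The conflict is real and limited. It is one grade wide and confined to acalabrutinib after the triggers in 6.2 and to severe tumor lysis or flare under Table 6. It is a direct contradiction when a cycle has been delayed, and an unstated precedence when the cycle starts on time. It should be corrected, since it concerns when patients are re-exposed to study drug.

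The conclusion rests on the wording alone. The documents do not say how often patients would be at grade 2 after such an event, so no number of affected patients can be given.

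A reader might infer three stronger things that the documents do not support:

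- **A one-grade gap for every non-hematologic event outside rash and neuropathy.** The other non-hematologic row of Table 6 and Section 6.6 both match 6.7.
- **Permanent stopping caused by the mismatch.** Section 6.2 says "Acalabrutinib should be discontinued in the event of an acalabrutinib toxicity lasting more than 28 day"s. That rule names no grade and does not depend on the restart threshold. A five-week acalabrutinib toxicity would meet it whether or not 6.7 had allowed dosing on Day 1.
- **A change in the ALO feasibility result.** The limit of 2 in 10 counts patients who stop treatment in the first year because of adverse events. The plan does not say whether stopping acalabrutinib alone counts, and it gives no frequency from which a shift could be estimated.

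**What to change.** Reconcile 6.2, Table 6, 6.3.2 and 6.7 so that each drug and each toxicity has a single restart threshold. State which section governs where a general and a drug-specific rule both apply, and make the restart sentence in 6.3.2 consistent with that statement. Correct the reference in 6.3.2 from 6.5 to 6.7. Check the cytopenia rules in 6.2, 6.4.1, 6.4.2 and 6.7 at the same time.

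The grade to require and the rule that should prevail are clinical decisions for the sponsor. The cost is a wording amendment, with no effect on sample size or analysis.
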